11.3. Estimands and Intercurrent Events

11.3.1. Primary Estimand and Supplementary Estimands of the Primary Objective

The primary estimand and the supplementary estimands for the primary objective will consider the effect of each individual EDP1815 cohort compared to the relevant placebo group (Cohort 1-3 Pooled Placebo for comparisons to C1-3 EDP1815 groups; and Cohort 4 Matched Placebo for comparison to the Cohort 4 EDP1815 group) on the percentage of participants achieving EASI-50 at Week 16.

The population summary measure of interest will be the odds ratio between each active EDP1815 treatment group and the relevant placebo group.

The FAS participant analysis set will be used.

Strategies for intercurrent events will be accounted for in the following manner using the relevant EDPS as follows:

Table 11-1: Intercurrent Event Strategies for the Primary and Supplementary Estimands

Estimand	Efficacy Data Point Set	Intercurrent Events		
		Use of Permitted Topical Corticosteroid Rescue Therapy	Study Discontinuation Before Week 16 Visit	Use of prohibited medications, non-compliance or unblinding Before Week 16
Primary Estimand	EDPS1	
If <28 days before Week 16 visit: Composite Strategy Participant will be considered a non-responder
 
If >28 days before Week 16 visit: Treatment Policy Strategy Data will be used as collected
	
If due to related reason: Composite Strategy Participant will be considered a non-responder
 
If due to non-related reason: While-on-treatment strategy No replacement of missing data
	
Treatment policy strategy: Data will be used as collected

Supplementary Estimand 1	EDPS2	
If <28 days before: While-on-treatment Strategy Data will be considered missing
 
If >28 days before: Treatment Policy Strategy Data will be used as collected
	As per primary estimand	As per primary estimand
Supplementary Estimand 2	EDPS3	
If <14 days before Week 16 visit: Composite Strategy Participant will be considered a non-responder
 
If >14 days before Week 16 visit: Treatment Policy Strategy Data will be used as collected
	As per primary estimand	As per primary estimand
Supplementary Estimand 3	EDPS4	As per primary estimand	While-on-treatment strategy: No replacement of missing data	As per primary estimand
Supplementary Estimand 4	EDPS5	As per primary estimand unless data is already excluded due to use of prohibited medications, non-compliance or unblinding	As per primary estimand unless data is already excluded due to use of prohibited medications, non-compliance or unblinding	While-on-treatment strategy Data collected after the intercurrent event will be excluded

Estimand	Efficacy Data Point Set	Use of Permitted Topical Corticosteroid Rescue Therapy	Intercurrent Events	Use of prohibited medications, non-compliance or unblinding Before Week 16
			Study Discontinuation Before Week 16 Visit	
Supplementary Estimand 5	EDPS6	Composite strategy Participants with use at any time between Day 1 and the Week 16 visit will be considered as non-responders.	As per primary estimand	As per primary estimand

11.3.2. Secondary Estimands

All continuous and response secondary estimands will use EDPS1 which uses a composite strategy for the use of topical corticosteroid rescue therapy less than 28 days before the relevant visit and for data missing due to withdrawal from the study due to a reason considered as related to study medication. For intercurrent events relating to compliance with the study medication, emollient use, unblinding or use of prohibited medications, a treatment policy strategy and data will be analyzed as collected.

Secondary endpoints based on the EASI, vIGA and PP-NRS endpoints will be analyzed with a supportive estimand using EDPS2, which uses a while-on-treatment strategy for rescue medication and excludes any data collected less than 28 days after rescue medication use. In addition, for responder endpoints relating to EASI, vIGA and PP-NRS a further supportive estimand using EDPS6 will be analyzed where all timepoints after any use of rescue medication will be considered as a non-responder.

Secondary count endpoints will use EDPS7 which includes all data as collected prior to completion or withdrawal from the study. As rescue medication use forms part of these endpoints it is not considered as an intercurrent event.

The following treatment differences will be estimated for each estimand in Cohorts 1-3:

- EDP1815 1.6x10¹¹ QD (Cohort 1) vs Cohorts 1-3 Pooled placebo
- EDP1815 6.4x10¹¹ QD (Cohort 2) vs Cohorts 1-3 Pooled placebo
- EDP1815 3.2x10¹¹ BID (Cohort 3) vs Cohorts 1-3 Pooled placebo
- EDP1815 6.4x10¹¹ Daily (Cohorts 2 and 3) vs Cohorts 1-3 Pooled placebo
- All EDP1815 (Cohorts 1, 2 and 3) vs Pooled placebo
- EDP1815 6.4x10¹¹ QD (Cohort 2) vs EDP1815 3.2x10¹¹ BID (Cohort 3)*
- EDP1815 1.6x10¹¹ QD (Cohort 1) vs EDP1815 6.4x10¹¹ QD (Cohort 2)*

* The final two comparisons between active treatment groups will be considered as exploratory and only estimates and confidence intervals of such comparisons will be shown.

The following treatment differences will be estimated for each estimand in Cohort 4:

- EDP1815 8.0x10¹⁰ QD (Cohort 4) vs Cohort 4 Matched Placebo
- EDP1815 8.0x10¹⁰ QD (Cohort 4) vs EDP1815 1.6x10¹¹ QD (Cohort 1)**

** The comparison between Cohort 4 and Cohort 1 active treatments will be performed on the primary and selected secondary endpoints in a separate model that also includes the EDP1815 1.6x10¹¹ QD (Cohort 1) treatment group, these comparisons will be considered as exploratory and only estimates and confidence intervals of such comparisons will be shown.

All secondary estimands will be evaluated at Weeks 4, 8, 12 and 16 unless otherwise specified.

Summary statistics only will be shown at Week 20 for those participants who completed treatment but did not wish to participate in the OLE.

Secondary efficacy estimands will be constructed for the following endpoints:

Table 11-2: Secondary Estimand Details

Data Type	Endpoint	Population Summary Measure of Interest
Continuous	Change and percentage change from baseline in EASI score ¹ , Change and percentage change from baseline in IGA*BSA ¹ Change and percentage change from baseline in BSA Change and percentage change from baseline in SCORAD score Change and percentage change from baseline in DLQI score Change and percentage change from baseline in POEM score, Change from baseline in PP-NRS ^{1,3} score Change from baseline in SD-NRS ²	Mean difference between treatments
Response	EASI-50 ^{1,2} , EASI-75 ^{1,2} , EASI-90 ^{1,2} IGA of 0 or 1 with a ≥ 2 point improvement from baseline ^{1,2} IGA of 0 or 1 ^{1,2} IGA of 0 (at Week 12 and 16 only) ^{1,2} BSA-50, BSA-75 BSA $\leq 3\%$ SCORAD-50, SCORAD-75 Improvement of ≥ 4 points in DLQI from baseline ⁴ Improvement of ≥ 2 and ≥ 4 points in PP-NRS score from baseline ^{1,2,3,4} Improvement of ≥ 2 points in SD-NRS score from baseline ^{3,4} Improvement of ≥ 4 points in POEM score from baseline ⁴ No requirement for rescue therapy ⁵	Odds ratio between treatments
Count	Number of courses of rescue therapy ⁶ Number of days requiring rescue therapy ⁵	Rate ratio between treatments

¹ These endpoints will also have secondary supplementary estimands using EDPS2, utilizing the same intercurrent event strategy as Supplementary estimand 1 for the primary endpoint.

² These endpoints will also have secondary supplementary estimands using EDPS6, utilizing the same intercurrent event strategy as Supplementary estimand 5 for the primary endpoint.

³ The score at each visit is calculated as the mean daily score for the 7 days prior to and including the visit date. At least 4 daily scores must be available for the score at the relevant visit to be considered evaluable.

⁴ Only for participants with relevant score ≥ 2 or ≥ 4 (as applicable) at baseline

⁵ Evaluated for Weeks 1-4, 5-8, 9-12 and 13-16 and for Weeks 1-16.

⁶ Evaluated for Weeks 1-8 and 9-16 and for and Weeks 1-16.

11.3.3. Exploratory Efficacy Estimands

Exploratory estimands will use the same intercurrent event strategy as the primary estimand, i.e., they will use the FAS and EDPS1 to give a composite strategy for the intercurrent event of topical

corticosteroid rescue therapy use <28 days before the evaluable timepoint and study discontinuation due to reasons relating to study medication and be estimated without regard to treatment compliance, any changes in background or rescue therapy or unblinding.

Exploratory estimands will be evaluated at all timepoints at which the relevant endpoints are collected.

Table 11-3: Exploratory Estimand Details

Data Type	Endpoint	Population Summary Measure of Interest
Continuous	Change and percentage change from Screening in EASI score Change from baseline in each of the SF-12 MCS and PCS scores Change from baseline in the ADCT scores Change from baseline in eosinophils and immune protein markers Change from baseline in immune cell RNA profile Change from baseline in PP-NRS score ¹ Change from baseline in SD-NRS score ¹	Mean value in each treatment group
Time to event (1)	Time to first achievement of EASI-50 Time to first achievement of IGA of 0 or 1 with a ≥ 2 point improvement from baseline Time to first achievement of sustained EASI-50 ²	Cumulative proportion to have achieved the event at each visit
Time to event (2)	Time to first achievement of a ≥ 2 point in improvement in PP-NRS score, in participants with a score of ≥ 2 at baseline Time to first achievement of a sustained ³ ≥ 2 point in improvement in PP-NRS score, in participants with a score of ≥ 2 at baseline Time to first achievement of a ≥ 4 point in improvement in PP-NRS score, in participants with a score of ≥ 4 at baseline Time to first achievement of a sustained ³ ≥ 4 point in improvement in PP-NRS score, in participants with a score of ≥ 4 at baseline Time to first achievement of a ≥ 2 point in improvement in SD-NRS score, in participants with a score of ≥ 2 at baseline Time to first achievement of a sustained ³ ≥ 2 point in improvement in SD-NRS score, in participants with a score of ≥ 2 at baseline	Kaplan-Meier estimates of proportion of responders at each week from 1 to 16.
Response (1)	IGA of 0 or 1 with a ≥ 2 point improvement from screening Improvement of ≥ 2 and ≥ 4 points in PP-NRS score from baseline ¹ Improvement of ≥ 4 points in SD-NRS score from baseline ¹	Proportion of responders at each timepoint
Response (2)	Development of skin infection requiring topical or systemic antibiotic treatment by Week 16	Proportion reporting at least one infection on or before the Week 16 visit.

¹ Evaluated daily from Day 2 to 112.

² Sustained EASI-50 is a response which is seen at least 2 consecutive visits.

³ Sustained PP-NRS or SD-NRS improvement is defined as the relevant improvement shown at all evaluable days within at least a 14-day period.

The primary and selected secondary response endpoints relating to EASI, IGA and PP-NRS endpoints will be used in exploratory estimands which compare those who received topical corticosteroid rescue medication within specific windows with those who used no topical corticosteroid rescue therapy. These estimands will use all data as collected with no imputation for intercurrent events.

For Cohort 4 only, the primary and secondary endpoints relating to EASI, IGA, IGA*BSA and PP-NRS (those endpoints flagged in Table 11-3 for the use of secondary supplementary estimands) will also be used for exploratory estimands which compare the Cohort 1 EDP1815 treatment group with the Cohort 4 EDP1815 treatment group.

11.3.4. Safety Estimands

All safety estimands will use the safety analysis set. A treatment policy approach will be used for all safety estimands, including all data collected regardless of treatment discontinuation, treatment compliance, changes in background or rescue therapy or unblinding of the subject.

SDPS1 will be used to estimate safety endpoints which are collected at scheduled visits.

SDPS2 will be used to estimate safety endpoints which are assessed at any time in the study.

Table 11-4: Safety Endpoint Details

Data Point Set	Endpoint	Population Summary Measure of Interest
SDPS1	Change from baseline in vital signs Change from baseline in ECG parameters Change from baseline in clinical laboratory parameters Change from baseline in physical examination findings	Summary statistics at each visit for each treatment group
SDPS2	Adverse events and serious adverse events Worst-case change from baseline with respect to potentially clinical important criteria for vital signs, QTcF and clinical laboratory parameters Worst-case change from baseline with respect to values outside the normal ranges for vital signs, ECG parameters and clinical laboratory parameters	Incidence in each treatment group

11.4. Planned Analyses

For all Cohort 1-3 analyses, data for the relevant endpoint will be analyzed within the same model and the Cohort 1-3 placebo groups will be pooled.

For all Cohort 4 analyses, the Cohort 4 EDP1815 data will be compared to the Cohort 4 Matched Placebo data. In separate models for the primary and selected secondary endpoints, the Cohort 1 EDP1815 data will be added to the model and compared to the Cohort 4 EDP1815 data; these analyses will be considered as exploratory.

11.4.1. Analysis of Primary Estimand

The primary estimand will be analyzed using a logistic regression with parameters for treatment group, baseline IGA score and baseline EASI score.

Body mass index, gender, race, and region will also be considered and included in the model if found to be significant.

The actual and predicted probability of EASI-50 response in each treatment group together with the estimated odds ratios and associated confidence intervals for each treatment difference will be displayed together with p-values for the comparisons of active treatment vs pooled placebo.

Actual and predicted probabilities of EASI-50 at Week 16 for each treatment group will be plotted.

11.4.2. Analysis of Supplementary Estimands on the Primary Objective

The four supplementary estimands defined for the primary objective will be analyzed in the same manner as the primary estimand.

For the potential covariates of body mass index, gender, race and region: those covariates found to be significant in the primary analysis will be included in all models regardless of significance in order to ensure comparability of the models.

11.4.3. Cohort 4 Sensitivity Analysis of the Primary Estimand

A Bayesian dynamic borrowing method using a commensurate prior will be used for the placebo comparator in the primary analysis model, utilizing all Cohort 4 data and Cohort 1-3 placebo data (Hobbs, Carlin, Mandrekar, & Sargent, 2011). In contrast to the primary analysis method, this sensitivity analysis will borrow information from the Cohort 1-3 placebo patients dependent on the similarity in outcomes between the Cohort 4 and Cohorts 1-3 placebo groups further sensitivity analyses for the primary and secondary endpoints may also be performed on the Cohort 4 data either using the same dynamic borrowing methodology or using the Cohort 4 only placebo group as the comparator. Full details are provided in the SAP.

11.4.4. Analysis of Secondary Estimands

Continuous secondary estimands will be analyzed using a mixed model for repeated measures (MMRM) with parameters for treatment group, visit, baseline IGA score and relevant baseline score and the interaction for treatment*visit.

For the potential covariates of body mass index, gender, race and region: those covariates found to be significant in the primary analysis will be included in all models regardless of significance in order to ensure comparability of the models.

Least squares mean estimates and their 95% confidence intervals (CI) will be presented for the endpoint value at each visit. Treatment differences between each EDP1815 group and the pooled placebo group will be estimated using LS mean differences, 95% CI and p-values. Pairwise treatment differences between EDP1815 groups will be estimated with LS mean differences and 95% CI.

Least square mean (95% CI) estimates will be plotted against visit. Least square mean (95% CI) treatment differences between each EDP1815 treatment group and the pooled placebo group will also be plotted against visit.

Response estimands will be analyzed with a generalized linear mixed effects model with a logit link function. Treatment, visit, baseline IGA and the appropriate baseline questionnaire score will be included as parameters together with the treatment*visit interaction. Odds ratios with 95% CIs and p-values for each EDP1815 group compared to the relevant pooled placebo group at each visit will be presented. Odds ratios and 95% CIs will be presented for any comparisons between two EDP1815 treatment groups.

In the event that there are no responders in one of the treatment groups at a visit, data from that visit will be excluded from the model and only summary statistics will be produced showing the number and percentage of responders at that visit.

Count estimands will be analyzed with a Poisson regression model fitted with treatment and baseline IGA as covariates. An offset of log (days in study) will also be included in the model to account for any data from participants who withdrew early from the study. If the distribution of the count data suggests over-dispersion and/or zero inflation, then other models including the negative binomial or zero-inflated Poisson model may be considered.

Model estimated event rates and their 95% confidence intervals will be presented for each treatment group. Rate ratios with 95% CIs and p-values for each EDP1815 group compared to the relevant pooled placebo group at each visit will be presented. Rate ratios and 95% CIs will be presented for any comparisons between two EDP1815 treatment groups.

11.4.5. Analysis of Exploratory Estimands

Exploratory endpoints will be summarized only. No inferential analysis is planned.

For the daily PP-NRS and SD-NRS endpoints which are evaluated daily only graphical summaries will be presented.

For the time to first response endpoints for the PP-NRS and SD-NRS scores, participants who have not met the response definition before the Week 16 visit will be censored at the Week 16 visit, or at the time of withdrawal from the study for those who withdrew before Week 16.

For the time to sustained response endpoints for the PP-NRS and SD-NRS scores, it will not be possible for participants to start a sustained response less than two weeks before the Week 16 visit. Therefore, such participants will be censored at 14 days before the date of the Week 16 visit or at the time of treatment withdrawal for participants who do not complete the 16-week treatment period.

For the primary and secondary responder endpoints relating to EASI, IGA and BSA, summaries will be provided comparing the number and percentage of participants in each treatment group who respond at Week 16 between the following 4 subgroups:

- Participants with no rescue therapy use
- Participants with no rescue therapy use after the Week 4 visit
- Participants with no rescue therapy use after the Week 8 visit
- Participants with no rescue therapy use within 4 weeks of the Week 16 visit
- Participants with no rescue therapy use within 2 weeks of the Week 16 visit
- Participants with rescue therapy use within 4 weeks of the Week 16 visit
- Participants with rescue therapy use within 2 weeks of the Week 16 visit

For these endpoints, all participants who have Week 16 data available for the relevant endpoint will be included and there will be no imputation for any intercurrent events.

For the Cohorts 1-3 analyses, pairwise treatment differences between two EDP1815 treatment groups will be estimated as part of the modelling done for the primary and secondary analyses, but such estimates will be considered as exploratory.

For the Cohort 4 analyses of the primary and selected secondary estimands, separate models will be used which include the EDP1815 1.6x10¹¹ (Cohort 1) treatment group in addition to the Cohort 4 EDP1815 8.0x10¹⁰ group and the Cohort 4 Matched Placebo group. From these tables, pairwise treatment differences between the two active EDP1815 groups will be estimated, with all such estimates being considered as exploratory.

11.4.6. Analysis of Safety Estimands

All safety data will be summarized by treatment group using the safety set and the data point set appropriate for the endpoint type.

11.4.7. Other Analyses

Tabulations will be provided for completion/withdrawal status, protocol deviations, study populations, demographic and other baseline characteristics, use of concomitant medications, and exposure to and compliance with IMP and emollients.

11.5. Handling of Protocol Deviations

Protocol deviations will be logged within the clinical trial management system and categorized dependent on the type of deviation and its significance.

Protocol deviations relating to the use of prohibited medications, to non-compliance with study treatment (including non-compliant emollient use) and to unblinding of the study before database lock will be accounted for as intercurrent events in the primary analysis.

11.6. Handling of Dropouts or Missing Data

Unless otherwise specified, missing data will be considered as missing at random and will be accounted for using mixed models for repeated measures, with all time points collected for the relevant endpoint included in the model.

Otherwise, missing data will not be imputed.

11.7. Planned Interim Analysis and Data Monitoring

An interim analysis may be undertaken prior to the end of recruitment for Cohorts 1,2 and 3. The purpose of this interim analysis is to check the sample size assumptions for placebo response rates and drop-out rates.

The balance of participants enrolled to each treatment group will also be checked during this analysis. Due to the use of stratification by IGA at baseline at both the cohort and treatment-within-cohort level, there may be up to 9 incomplete blocks of treatment assignments remaining at the end of randomization. This may lead to imbalance between the cohorts and/or treatment groups. An unblinded team within the Biostatistical Vendor will review the overall numbers of participants randomized to each treatment group and as a result may specify to the IRS Vendor that the randomization numbers for an individual cohort and/or the randomization numbers for an

individual treatment within a cohort are restricted and no longer available for use for the remaining participants to be randomized. The aim of this will be to ensure that each of the four treatment groups has a minimum of 73 randomized participants.

Blinded analyses of eCOA data will be performed during the recruitment period. As a result of these, possible changes in the conduct of the study may be to stop recruitment from one or more of the baseline IGA severity strata. No other changes to study conduct are expected.

The data for Cohorts 1, 2 and 3 will be locked, unblinded and analyzed before the end of Cohort 4.

11.8. Determination of Sample Size

Cohorts 1-3

The sample size was calculated using the assumption that data from the placebo participants in the three cohorts can be pooled prior to comparison with the EDP1815 treatment groups. No adjustments for multiple testing have been made.

The primary efficacy endpoint is the achievement of EASI-50 at Week 16. The pooled placebo response rate is estimated to be approximately 25% and a doubling of this to 50% for EDP1815 would be considered as clinically meaningful.

Using a two-sided test at the 5% level of significance, 58 participants in each treatment group would give 80% power to detect a difference in one of the EDP1815 cohorts compared to the pooled placebo group. There would also be more than 90% power to compare the pooled EDP1815 6.4×10^{11} daily dose or all the EDP1815 group to the pooled placebo group.

Under the assumption of a 20% drop-out of participants prior to Week 16 this will require a total of at least 73 participants to be enrolled in each treatment group. In order to allow for the 3:1 randomization in each cohort this has been adjusted to 75 participants per treatment group to give a total of 300 participants recruited. With 75 EDP1815 participants and 25 placebo participants in each of the three cohorts.

Cohort 4

Using the same assumptions relating to the placebo rate, clinically meaningful difference, significance level, and drop-out rate as above for Cohorts 1-3, approximately 70 participants are required in each of the EDP1815 8.0×10^{10} and Cohort 4 Matched Placebo groups to provide approximately 80% power in detecting a difference between EDP1815 and placebo in Cohort 4.

In order to allow 50% of the placebo control group to be concurrent controls and 50% to be historic matched controls from Cohorts 1-3, a 2:1 randomization will be used to enroll 70 EDP1815 8.0×10^{10} subjects and 35 placebo participants to Cohort 4.

If sensitivity analyses indicate that pooling of the Cohort 4 placebo group with the Cohort 1-3 matched placebo data is inappropriate, then the power of the comparison between the Cohort 4

EDP1815 and placebo groups is approximately 65% if only Cohort 4 placebo participants could be used in the treatment comparisons.

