Under the assumption of a 20% drop-out of participants prior to Week 16 this will require a total of at least 73 participants to be enrolled in each treatment group. In order to allow for the 3:1 randomisation in each cohort this has been adjusted to 75 participants per treatment group to give a total of 300 participants recruited. With 75 EDP1815 participants and 25 placebo participants in each of the three cohorts.

Cohort 4

Using the same assumptions relating to the placebo rate, clinically meaningful difference, significance level, and drop-out rate as above for Cohorts 1-3, approximately 70 participants are required in each of the EDP1815 8.0×10^{10} and Cohort 4 Matched Placebo groups to provide approximately 80% power in detecting a difference between EDP1815 and placebo in Cohort 4.

In order to allow 50% of the placebo control group to be concurrent controls and 50% to be historic matched controls from Cohorts 1-3, a 2:1 randomization will be used to enroll 70 EDP1815 8.0×10^{10} subjects and 35 placebo participants to Cohort 4.

If sensitivity analyses indicate that pooling of the Cohort 4 placebo group with the Cohort 1-3 matched placebo data is inappropriate, then the power of the comparison between the Cohort 4 EDP1815 and placebo groups is approximately 65% if only Cohort 4 placebo participants could be used in the treatment comparisons.

7 General Considerations

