4.5 Exploratory Efficacy Analyses

The exploratory efficacy analyses described in the main SAP will also be produced for cohort 4.

5 Technical Details

In addition to the technical details of processes described in the main SAP where [REDACTED] team is involved, the Bayesian dynamic borrowing sensitivity analysis of the primary endpoint will be conducted by [REDACTED] utilizing RBest package in R.

6 Summary of Changes from the Protocol

The SAP Addendum is based on the latest Protocol v5.0.

Table 1: Summary of Changes from the Protocol and the main SAP

Protocol Version	Summary of Change	Justification for change
V5.0	Protocol states the sensitivity analysis for the primary endpoint of Cohort 4 will utilize a commensurate prior method to perform dynamic borrowing. The approach has been updated to utilize robust mixture priors to perform the dynamic borrowing sensitivity analysis	The robust mixture priors method is more robust due to the inclusion of a weakly informative component in the prior distribution
V5.0	Sensitivity analysis to compare cohort 4 EDP1815 to a cohort 4 placebo was added.	Due to the concerns in cohorts 1-3 placebo participants similarity to cohort 4 placebo, it was decided to add sensitivity analysis (within cohort 4 comparison). So in the case of different behaviour of cohort 4 placebo participants, sensitivity analysis vs. cohort 4 placebo still will be valid, however, with less power (as described in the Protocol).

7 Bibliography

- Austin, Peter C. 2011. *Optimal caliper widths for propensity-score matching when estimating differences in means and differences in proportions in observational studies*. Pharm Stat. 2011 Mar; 10(2): 150–161. doi:10.1002/pst.433.
- Beat Neuenschwander, Sebastian Weber, Heinz Schmidli, Anthony O'Hagan. 2020. *Predictively consistent prior effective sample sizes*. doi: <https://doi.org/10.1111/biom.13252>.
- Heinz Schmidli, Sandro Gsteiger, Satrajit Roychoudhury, Anthony O'Hagan, David Spiegelhalter, Beat Neuenschwander. 2014. *Robust meta-analytic-predictive priors in clinical trials with historical control information*. doi: <https://doi.org/10.1111/biom.12242>.

8 Appendix 1: List of Tables, Figures and Listings

Only additional outputs not listed in the main SAP included in this section.

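### Is the stated power of about 65% for Cohort 4 EDP1815 against its own placebo too high?

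*Protocol*

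**What the plan says.** For Cohorts 1-3, Protocol section 11.8 states the planning rates: "The pooled placebo response rate is estimated to be approximately 25% and a doubling of this to 50% for EDP1815". It then gives the size and power: "Using a two-sided test at the 5% level of significance, 58 participants in each treatment group would give 80% power". Drop-out is added as follows: "Under the assumption of a 20% drop-out of participants prior to Week 16 this will require a total of at least 73 participants".

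The Cohort 4 part of the same section opens with "Using the same assumptions relating to the placebo rate, clinically meaningful difference, significance level, and drop-out rate as above for Cohorts 1-3". It asks for about 70 participants in each of the EDP1815 and matched placebo groups for about 80% power, and it sets a 2:1 randomisation of 70 to EDP1815 and 35 to placebo. If borrowing proves inappropriate, it states the power that remains: "EDP1815 and placebo groups is approximately 65% if only Cohort 4 placebo participants could be used in the treatment comparisons". SAP section 6 carries the same text, ending "placebo groups is approximately 65% if only Cohort 4 placebo participants could be used in the treatment comparisons".

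The SAP Addendum (section 6) adds the comparison within Cohort 4 because of doubts about how similar the placebo groups are. It says that the "sensitivity analysis vs. cohort 4 placebo still will be valid, however, with less power (as described in the Protocol"), and it does not restate a number.

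**The concern.** The Cohort 4 text says that it carries over the Cohorts 1-3 assumptions, so a reader will try to reproduce every figure in the section with one formula. The 58 per group comes out of the pooled-variance formula and not out of the unpooled one, which needs 55. Applied to 56 against 28, the pooled formula gives about 60% instead of 65%. It is natural to conclude that the method changed between the two calculations, or that the 65% is a slip.

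The comparison matters because it is the only Cohort 4 contrast against placebo that is wholly concurrent and randomised, and it is the one to fall back on if borrowing fails. If its power were 60%, the type II error would be 40% instead of 35%, and a non-significant result would say less than the reader had been told.

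**Working it through.** **Inputs (Protocol 11.8).** Response 25% on placebo and 50% on EDP1815; two-sided 5%; 20% drop-out; 70 and 35 randomised. Evaluable: 70 × 0.8 = 56 and 35 × 0.8 = 28, if every drop-out is missing at Week 16.

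**1. The stated 65%, unpooled variance.** Power = Φ(d/SE − 1.960).

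- SE = √(0.25 × 0.75/28 + 0.50 × 0.50/56) = √(0.00670 + 0.00446) = 0.1056
- 0.25/0.1056 = 2.366, and 2.366 − 1.960 = 0.406
- Φ(0.406) = 65.8%

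The plan's figure is reproduced.

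**2. The neighbouring Cohort 4 figures, same formula.**

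- n per group = (1.960 + 0.842)² × (0.1875 + 0.25)/0.25² = 54.9, so 55. Then 55/0.8 = 68.75, so 69. The plan says about 70.
- At 56 against 56, SE = √(0.4375/56) = 0.0884. Then 0.25/0.0884 = 2.828, and Φ(2.828 − 1.960) = 80.7%. The plan says about 80%.

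All three Cohort 4 figures follow from one formula.

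**3. The pooled formula.** Power = Φ((d − 1.960 × SE₀)/SE₁).

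- p̄ = (28 × 0.25 + 56 × 0.50)/84 = 0.4167
- SE₀ = √(0.2431 × (1/28 + 1/56)) = 0.1141, and SE₁ = 0.1056 as above
- (0.25 − 0.2237)/0.1056 = 0.249, and Φ(0.249) = 59.8%

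**4. The formulas side by side.**

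| Formula | n per group for 80% | 58 vs 58 | 56 vs 56 | 56 vs 28 |
|---|---|---|---|---|
| Pooled | 58 | 80.2% | 78.8% | 59.8% |
| Arcsine | 58 | 80.5% | 79.1% | 61.9% |
| Unpooled | 55 | 82.1% | 80.7% | 65.8% |

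The 58 does not identify the pooled formula, since arcsine gives it too. The pooled formula also fits the Cohort 4 text less well: it needs 58/0.8 = 72.5, so 73 enrolled, where the plan says about 70.

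**5. Exact enumeration at 56 against 28, without covariates.** Logistic Wald 60.7%, chi-square 61.1%, likelihood ratio 62.1%, unpooled z 65.6%.

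**6. How firm is 56 against 28?** The primary estimand (Protocol 11.1.2 and 11.3.1; SAP 7.1.2.1 and 9.3.1) counts withdrawals for treatment-related reasons as non-responders and keeps them in the analysis. Only unrelated withdrawals are missing. The documents do not split the 20%. Suppose that half are related, and that 25% and 50% already describe the composite endpoint. Then 70 × 0.9 = 63 and 35 × 0.9 = 31.5, taken as 31, are analysed. The pooled formula gives p̄ = 39.25/94 = 0.4176, SE₀ = 0.1082 and SE₁ = 0.1001, hence Φ((0.25 − 0.2121)/0.1001) = 64.8%.

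**7. Covariates.** The planned model adjusts for baseline vIGA and EASI (Protocol 11.4.1; SAP 9.3.3). Simulation of an adjusted logistic model at these rates gave about 60% to 69%, depending on how strongly the covariates are assumed to predict response. The documents give no value for that strength.

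**The case for a change.** The strongest case against the 65% is that the planned test is a logistic regression, not an unpooled z-test. Unadjusted tests near to it have exact power of about 61% to 62%. The unpooled z-test that reaches 65.6% has an actual type I error of about 6.2% when both rates are 25%, above the nominal 5%. The two variance formulas nearly agree at equal allocation (78.8% against 80.7%) but separate at 2:1 (59.8% against 65.8%), so the choice matters most for exactly this figure. Drop-out does not explain the gap: with none at all, 70 against 35 gives 70.2% pooled and 75.4% unpooled.

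Two things stand. Among the formulas tried, no single one gives both the 58 and the 65%. And an unadjusted analysis with every drop-out missing would have power some 3 to 5 points below the stated figure.

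Neither makes the figure wrong. The sentence that carries assumptions over to Cohort 4 lists the placebo rate, the difference, the significance level and the drop-out, and says nothing of a formula. Cohort 4 was added by a later amendment (Protocol section 17), so its calculation need not share a formula with the earlier cohorts. The unadjusted figures leave out the planned covariates, and they treat as missing some withdrawals that the estimand keeps. Either factor can close the gap.

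**Conclusion.** The concern does not hold. The stated 65% follows from the plan's own inputs by a standard formula (65.8%), and that formula also yields the about 70 per group and the about 80% beside it. A value of 60% requires a pooled method that the documents do not name. Replacing 65% with 60% would exchange one undocumented formula for another and leave the about 70 per group less well matched.

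The range is about 60% to 66% for the three approximations and the exact tests in the working, with 56 against 28 evaluable. It is about 60% to 69% for an adjusted logistic model under assumed covariate strengths. The plan's approximate 65% lies inside both. These ranges rest on response rates of 25% and 50%, a two-sided 5% level and all drop-outs missing at Week 16.

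Nothing depends on the difference. Enrolment of 70 and 35 was set for the matched comparison, the fallback power triggers no decision, and both the Protocol and the Addendum already tell the reader that this comparison has reduced power.
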